10.12. Reporting a Serious Adverse Event

Any SAE, including death due to any cause, that occurs during this study, whether or not believed to be related to the study medication, must be reported immediately (within 24 hours of knowledge of the event) by:

1. Entering the adverse event in the appropriate section (AE page and/or SAE page) of the eCRF, indicating that the event is considered serious, and providing all the details per the eCRF completion guidelines.

AND

2. Completing the SAE Report Form and emailing or faxing to PAREXEL Safety Services.

In the event that the site is unable to complete the SAE form or eCRF entry to report the event within 24 hours of their knowledge of the event, investigators may report the SAE to PAREXEL Safety Services over the telephone. Then the eCRF must be completed or the SAE Report Form must be emailed within the following 24 hours.

Sites may obtain assistance with SAE reporting procedures or the specifics of reporting an event by calling PAREXEL Safety Services.

Serious Adverse Event Reporting		
PAREXEL Safety Services	[contact] [contact]	[contact]
Specific medical questions can be addressed to the Enterin Medical Director:		
[name], MD	[contact]	[contact]

The initial report should contain as much information as is available concerning the event in order to permit the Sponsor to file a report that satisfies regulatory requirements. Initial telephone reports of serious adverse events must be followed-up by completion of the AE/SAE eCRF or emailing the completed SAE Report Form as described above. When additional information is available, the investigator should provide an appropriate supplementary event narrative to PAREXEL Safety Services.

All appropriate SAEs will be reported to the appropriate regulatory authorities and central IRB by PAREXEL Safety Services within specified timelines. A copy of all FDA reportable serious adverse events will be mailed to all investigators participating in ongoing

clinical studies with the study medication in order to permit prompt notification of the appropriate local IRB where required.

10.13. Departure from Protocol for Emergency or Adverse Event

In medical emergencies, the investigator should use medical judgment and remove the subject from immediate hazard. As soon as possible after removing the subject from hazard, the investigator must contact Enterin Inc. by telephone to permit a decision as to whether the subject may continue in the study. The IRB should also be notified as to the type of emergency and the course of action. The CRF for the subject must describe the departure from the protocol and state the reason.

10.14. Safety Monitoring

A Data Safety and Monitoring Board (DSMB) has been established to monitor the safety of the subjects during the study. The DSMB includes members with relevant clinical expertise, including a good understanding of the safety of medications for Parkinson's disease. These members include a statistician, a gastroenterologist, and a neurologist. The methodology and the operating procedures for the safety reviews will be developed by the Chairperson in collaboration with the sponsor and will be documented in the DSMB Charter.

10.15. Stopping Rules

It is anticipated that no more than 2 subjects out of 50 (4.0 %) will have an AE of Grade 4 or Grade 5 that is at least possibly related to ENT-01 in this Study. Should there be more than 2 subjects with an AE grade 4 or 5 that is at least possibly related to ENT-01 in the cohort of subjects, the study will be put on an immediate clinical hold. Safety Monitoring processes are identified in [Section 10.14](#).

In addition, individual safety stopping criteria will include:

- Reaching DLT before a prokinetic effect
- Serious Adverse Event at least possibly attributable to ENT-01.
- Having a non-DLT gastrointestinal adverse event > grade 3 within 24 hours of taking ENT-01 that is at least possibly attributable to ENT-01
- A fall in systolic blood pressure to < 80 mm Hg upon rising from lying to sitting or standing
- A fall in diastolic blood pressure to < 40 mm Hg upon rising from lying to sitting or standing

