2. OBJECTIVES AND ENDPOINTS

2.1. Primary Safety Objective

To determine the safety and tolerability of orally administered ENT-01 for approximately 14 weeks in subjects with Parkinson's disease-related constipation.

Safety endpoints will include adverse events as evaluated with subject self-reporting, vital signs, clinical chemistry and hematology blood analyses, urinalysis, and electrocardiogram (EKG).

During the dosing period, it is anticipated that no more than 2 subjects out of 50 (4.0%) will have an adverse event of grade 4 or 5 that is at least possibly related to ENT-01. Should there be more than 2 subjects with an adverse event grade 4 or 5 that is at least possibly related to ENT-01 in the cohort of subjects, the study will be put on an immediate clinical hold. Safety Monitoring processes are identified in [Section 10.14](#).

In addition, individual safety stopping rules will include:

- Reaching dose-limiting tolerability (DLT) before a prokinetic effect
- Having a non-DLT gastrointestinal adverse event > grade 3 within 24 hours of taking study medication that is at least possibly attributable to ENT-01

Tolerability

Tolerability endpoints are referred to as the DLT and will include:

- Recurrent vomiting defined as 3-5 episodes of vomiting within 24 hours of taking study medication (i.e., a Grade 2 or higher AE, see [Table 2](#)).
- Recurrent diarrhea defined as 7 episodes of diarrhea within 24 hours of taking study medication on 2 consecutive days (i.e., a Grade 3 or higher AE, see [Table 2](#)).
- Dizziness defined as lightheadedness or fainting on rising from lying to sitting or standing that requires non-urgent medical intervention within 24 hours of taking study medication. (i.e., a Grade 2 or higher AE see [Table 2](#)).

It is anticipated that all subjects will exhibit a prokinetic effect at a dose lower than DLT and less than or equal to 250mg. Subjects reaching DLT before a prokinetic effect will be treated at the highest dose at which they did not experience a DLT.

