Subjects will keep daily electronic stool diaries and will record information concerning stools immediately after each bowel movement, including stool frequency, consistency, ease of evacuation, completeness, and the use of rescue medication. Site staff will monitor these entries regularly to ensure subjects are not at risk of becoming impacted and are using rescue medication appropriately. Site staff will contact subjects if the web-based questionnaires are not being completed on a daily basis or if there are any safety concerns.

Each subject will be started on a pre-defined dose based upon their baseline CSBM rate during the randomized study, then will be able to increase their dose every 2-3 days until they reach a pro-kinetic dose or the maximum dose of 250mg. This is called the Dose Escalation Period (DEP). After the subject documents 4 CSBMs over 5 consecutive days, the subject will fix at that dose for the remainder of the study. This is called the Fixed Dose Period (FDP). At the end of the FDP medication will be discontinued and a 6-week wash-out period (WOP) will follow. Daily stool e-diary will be entered throughout the dosing period.

Rescue medications (including oral Bisacodyl, suppositories, and enemas,) will be provided to subjects and will be initiated in the evening of the third day if a subject has had no bowel movement for three consecutive days.

Study medication will be taken on an empty stomach first thing in the morning with 8 oz water and no food will be allowed for 60 minutes. Subjects prescribed levodopa should wait at least 30 minutes between taking levodopa and study medication. Tea and coffee with/without milk/sugar and orange juice (without pulp) are permitted. Plain yoghurt can be added if the patient experiences repeated nausea.

Symptoms of Parkinson's disease will be assessed using the Unified Parkinson's disease Rating Scale (MDS-UPDRS, Parts I-III) by certified raters and patients with fluctuations and prescribed levodopa will be assessed during "ON" states, approximately one hour after levodopa intake.

Subjects who prematurely discontinue study drug for any reason will be asked to have an Early Termination (ET) visit within 3 days following the last study drug dose. If a subject discontinues study drug during a scheduled visit, then the Early Termination visit will be conducted at that time. (Early Termination visit assessments are the same as Visit 4.)

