The dose will be taken upon awakening on an empty stomach along with 8 oz. of water. Subjects prescribed levodopa should wait at least 30 minutes between taking levodopa and study medication. The subject will be instructed to not eat for at least 60 minutes after study drug administration. Tea, coffee with/without milk/sugar and orange juice (without pulp) are permitted. Plain yoghurt can be added if the patient experiences repeated nausea. Dosing will be increased every 2-3 days until a pro-kinetic dose or the maximum dose is reached. If the subject has not

produced a CSBM within 24 hours on at least 4 of 5 consecutive days, then they will increase their daily dose by 1 tablet (by 25 mg). This incremental dosing will continue until the subject:

- reaches the prokinetic dose (the dose producing a CSBM within 24 hours on at least 4 of 5 consecutive days). The subject then remains on that dose until Visit 4;
- reaches the maximum dose of 10 tablets (250mg for active treatment); or,
- reaches the dose limiting tolerability (DLT).

If the subject has 7 or more discrete episodes of diarrhea separated by 30 minutes or more within 24 hours at any dose on 2 consecutive days, the dose will be reduced by 25mg and fixed at that dose (assuming the diarrhea abates at the lower dose).

Should a prokinetic response not occur at the maximum allowed number of tablets (10 tablets or 250mg), subjects will continue to take 10 tablets throughout the Fixed Dose period.

Site staff will review subject diary entries daily and contact subjects as needed to ensure subject safety, compliance with study and dosing instructions, and to determine the subject's individual fixed dose level. The day that a subject "fixes" their dose for the first time (as determined by site staff) is considered Day 1 for the purposes of scheduling subsequent study visits.

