10.3. CTCAE Definitions of Dose Limiting Adverse Events

Table 2: NCI CTCAE v. 4.03 Definitions for DLT Adverse Events

Adverse Event	Grade 1	Grade 2	Grade 3	Grade 4	Grade 5
Diarrhea (watery stool)	Increase of <4 stools a day over baseline	Increase of 4-6 stools a day over baseline	Increase of >7 stools a day; incontinence; hospitalization indicated	Life threatening complications: urgent intervention indicated	Death
Vomiting	1-2 episodes per 24 hours	3-5 episodes per 24 hours	6 or more episodes in 24 hours; tube feeding, TPN or hospitalization indicated	Life-threatening consequences: urgent intervention indicated	Death
Postural hypotension ³	Mild, transient lightheadedness or dizziness upon rising from lying or sitting position that does not interfere with ADL	Moderate lightheadedness, dizziness or fainting upon rising from lying or sitting position that limits instrumental ADL; Non-urgent medical intervention indicated	Severe lightheadedness, dizziness or fainting upon rising from lying or sitting position that limits self-care ADL; Medical intervention or hospitalization indicated	Life-threatening and urgent intervention indicated	Death

³Definition adapted from combining CTCAE definitions for Hypotension and Dizziness

10.4. Criteria for Dose Limiting Toxicity (DLT) Endpoints:

- Recurrent vomiting: 3-5 episodes of vomiting within 24 hours of taking study medication (Grade 2 adverse event)
- Recurrent diarrhea: >7 episodes of diarrhea within 24 hours of taking study medication (Grade 3 adverse event)
- Dizziness: Moderate lightheadedness or fainting upon rising from lying to sitting or standing and severe enough to require medical intervention within 24 hours of taking study medication (Grade 2 adverse event) or either a systolic blood pressure less than 80mmHg or diastolic blood pressure less than 40mm Hg.

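### After dose fixing, a responder with non-serious DLT vomiting or DLT dizziness has no written dose-reduction option, and the DLT summary stops before the Fixed Dose Period

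*Combined protocol and SAP*

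**What the plan says.** The individual safety rules in Section 10.15 begin with "Reaching DLT before a prokinetic effect"; Section 2.1 has the matching entry "Reaching dose-limiting tolerability (DLT) before a prokinetic effect". Section 2.1 later says what happens to these subjects: "Subjects reaching DLT before a prokinetic effect will be treated at the highest dose at which they did not experience a DLT". Both the stop and the step-down carry the same condition.

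Once a subject responds, Section 3 says "the subject will fix at that dose for the remainder of the study", and Section 3.2 says "The subject then remains on that dose until Visit 4". The one dose reduction written broadly enough to reach past escalation is for diarrhea: seven or more episodes "within 24 hours at any dose on 2 consecutive days, the dose will be reduced by 25mg and fixed at that dose" (Section 3.2).

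Section 2.1 makes the DLT events (vomiting, diarrhea, dizziness) the tolerability endpoints, under an objective covering about 14 weeks. Section 11.4 summarises them by dose level for the Dose Adjustment period only.

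**The concern.** The study exists to add duration: Section 1 says that length of dosing is all that separates it from the two previous studies. The added time is almost entirely the Fixed Dose Period, yet there the DLT rule switches off for anyone who has responded.

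Two things are at stake. First, sites facing the same event may continue the dose or withdraw the subject, and some may reduce the dose without a rule to support it. That affects the subject, and it also makes event duration, dose changes and discontinuations harder to interpret. Second, a DLT table that ends with dose adjustment does not describe the named tolerability endpoint over the period the objective covers.

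**Working it through.** The plan's only sample-size figure is the 92% chance of seeing at least one event with a 5% rate in 50 subjects (Section 11.7). It reproduces: 1 - 0.95^50 = 0.923. The present point does not depend on it.

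**Step 1: apply each rule to a fixed-dose responder.** Case A is related DLT vomiting not judged serious. Case B is related DLT dizziness not judged serious, with systolic pressure at least 80 and diastolic at least 40 mm Hg.

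| Rule | Case A | Case B |
|---|---|---|
| DLT stop (2.1, 10.15) | No: prokinetic effect already reached | No: same reason |
| DLT step-down (2.1) | No: same condition | No: same condition |
| Related-SAE stop (10.15) | No: not serious | No: not serious |
| Non-DLT GI event above grade 3 (2.1, 10.15) | No: a DLT, and grade 2 or 3 | No: not GI |
| Blood pressure stops (10.15) | Not relevant | No: above both limits |
| Diarrhea reductions (3.2) | No | No |
| Hold the dose to Visit 4 (3, 3.2) | Applies | Applies |

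The GI rule misses Case A on either reading. Section 10.4 defines DLT vomiting as 3-5 episodes, while 2.1 adds grade 2 or higher. If grade 3 vomiting is not a DLT, it still fails the requirement of a grade above 3.

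**Step 2: who is outside the gap.** Diarrhea has its own step-down. Serious related events and pressures below the limits are stopped. Subjects fixed at 250 mg without response, or fixed because of a DLT, are still before a prokinetic effect, so Section 2.1 covers them.

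**Step 3: what else could supply a dose reduction.** Section 6 allows withdrawal on clinical judgment. Section 10.13 covers medical emergencies. Section 13.8 allows departures only for an immediate hazard, and 13.9 rules out waivers. Sections 10.8 and 11.3 record dose changes and tabulate interruptions without saying when to make one. Read literally, lowering a responder's dose for grade 2 vomiting is a deviation.

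**Step 4: stop or continue.** "Reaching DLT before a prokinetic effect" sits in a stopping list, but "Subjects reaching DLT before a prokinetic effect will be treated at the highest dose at which they did not experience a DLT" keeps the same subject on drug. Section 3.2 agrees with continuing, since there a DLT only ends escalation.

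**Step 5: share of dosing without a DLT summary.** The Fixed Dose Period is 12 x 7 = 84 days. Escalation is about 14 days (Section 3) and at most 20 (Appendix 2).

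- 84 / (84 + 14) = 84/98 = 0.857
- 84 / (84 + 20) = 84/104 = 0.808

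This takes the Dose Adjustment period to mean the Dose Escalation Period. Appendix 2 has no period of the former name, but exclusion criterion 3 uses it in a way that fits.

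**The case against.** The strongest reply is that the gap is narrow and clinical judgment can fill it. Much of this stands.

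- Section 10.11 widens seriousness beyond the list in 10.9 to events the investigator thinks suggest a significant hazard, contraindication or precaution. If related, these trigger the SAE stop. Table 2 also ties grade 3 vomiting to "6 or more episodes in 24 hours; tube feeding, TPN or hospitalization indicated", so much of it would be serious. What remains is mainly grade 2 vomiting, and grade 2 dizziness without severe hypotension.
- Section 3.2 refers to the day a subject first fixes the dose, which hints that re-fixing is possible. It gives no trigger for vomiting or dizziness, so it does not close the gap.
- Section 11.3 reports adverse events by preferred term and period, including the Fixed Dose Period. What is missing is the DLT-defined summary, not the events.
- The separate SAP named in Section 11.2 is not among the documents. It could add the table, but a SAP would not normally supply a clinical dosing rule.

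A reader might infer that fixed-dose subjects are unprotected, or that their vomiting and dizziness would go unreported. The rules above contradict both.

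A reader might also try to count affected subjects from the 82.4% Phase 2a response. That endpoint was a gain of 1 CSBM/week, or 3 CSBM/week. The prokinetic criterion here is a CSBM on at least 4 of 5 days, or 4/5 x 7 = 5.6 days with a CSBM per week, which is far stricter. Nor is moderate dizziness in 1 of 44 Phase 2a subjects (2.3%, exact 95% CI 0.06-12.0%) a post-fixing rate: its timing relative to fixing is not given, and the patient was on an alpha-blocker. That patient was withdrawn and recovered.

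**Conclusion.** The point holds in a limited form. A fixed-dose responder with related DLT vomiting or dizziness, not judged serious and above both pressure limits, has no written route to a lower dose. The choices on paper are to continue or to withdraw, apart from emergencies and DSMB oversight. The stopping lists also conflict with the step-down in Section 2.1. Under Section 11.4 the DLT endpoint is not tabulated for 81-86% of dosing, assuming 14 to 20 days of escalation and that Dose Adjustment means Dose Escalation.

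How many subjects this touches cannot be estimated. The documents give neither a post-fixing DLT rate nor an observed rate for the 4-of-5-day criterion; Section 2.1 only anticipates that all subjects will respond below DLT. The change is worth making because the gap falls on the primary safety objective and is cheap to close. It does not show that the study is unsafe or its adverse event data incomplete.

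**What to change.** (a) Extend the Section 11.4 DLT summary to the Fixed Dose Period.

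(b) Take DLT out of the stopping lists in 2.1 and 10.15 and make it a dose-modification rule. A related DLT, before or after fixing, allows a 25 mg reduction, as already written for diarrhea, or a return to the highest dose without a DLT. Discontinuation on recurrence is left to the investigator. The related-SAE and blood pressure stops take precedence.

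(c) Amend Sections 3 and 3.2 so that a responder's dose may be lowered after fixing.

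The 25 mg option matters because a responder fixed at the starting dose has no lower dose taken in this study to return to. From 150 mg it gives 125 mg. From 75 mg it gives 50 mg, which Table 1 does not list, so the amendment should either add that dose or name 75 mg as the floor.

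The cost is one protocol amendment, with IRB approval and FDA submission under Section 10.17. No new visits or data items are needed, since severity, relatedness and dose changes are already recorded under 10.8. A few subjects may end on a lower fixed dose, with possibly some loss of bowel effect; the documents do not allow that loss to be quantified.

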10.16. Follow-Up and Final Reports

The investigator shall provide Enterin, Inc. with an accurate final report within 1 month after completion, termination or discontinuation of the study. The final report may not precede retrieval of CRFs which have not been monitored.

10.17. Regulatory Aspects

Neither the investigator nor Enterin Inc. shall modify this protocol without first obtaining concurrence of the other in writing. All changes must be submitted to the IRB. Protocol modifications which impact subject safety, or the validity of the study must be approved by the IRB and submitted to the FDA before implementation. In the case of a medical emergency to increase safety of subjects, a change may be made after discussion with the sponsor. In these instances, the IRB and FDA will be notified as soon as possible.

11. DATA MANAGEMENT AND STATISTICS

11.1. Populations for Analyses

The following populations will be considered for statistical analyses.

- **Safety Population:** The Safety Population will consist of all subjects who receive at least one dose of study drug.
- **Fixed Dose Population:** The Fixed Dose Population will include all subjects who are in Safety Population who enter the Fixed Dose period of the study.
- **Efficacy Evaluable Population:** The Efficacy Evaluable Population will include all subjects in the ITT Population who complete their Fixed Dose period with no major protocol violations.

11.2. Analysis Methods

General Methods

Details of the statistical analysis methodology will be provided in a separate statistical analysis plan (SAP), which will be finalized prior to the interim analysis being performed.

Continuous variables will be summarized using the number of observations, number of observations above the limit of quantification (if applicable), mean, standard deviation (SD) median, and range. Categorical variables will be summarized using frequency counts and percentages.

Analysis of Subject Disposition, History, and Baseline Characteristics

Subject disposition, including analysis population allocation, subjects enrolled, completed each period, discontinued, and primary reason for discontinuation, will be summarized using frequency and percentage. Protocol deviations will be summarized using frequency and percentage. Medical history data and prior and concomitant medications will be summarized using frequency and percentage. Subjects' age, height, weight, and baseline disease characteristics will be summarized using descriptive statistics. Gender, race, and other categorical variables will be provided using frequency and percentage.

11.3. Safety Analyses

All safety analyses will be performed on the Safety Population. The safety data will be presented in individual listings and summary tables.

Adverse Events

AEs will be coded according to the latest version of the Medical Dictionary for Regulatory Activities (MedDRA). The intensity/severity of AEs will be graded according to NCI-CTCAE v.4.03.

TEAEs, AEs leading to study treatment discontinuation, AEs leading to dose interruption, AEs related to study medication, SAEs, and AEs leading to death will be summarized by system organ class, preferred term, and study period (Screening, dose escalation, Fixed Dose, Wash-Out). A summary of AEs that are CTCAE Grade 3 or higher, as well as the most frequent preferred terms, will be provided.

If a subject experiences the same preferred term multiple times within a period, then the event will be counted only once within the period and by greatest severity.

Descriptive statistics will be used to summarize the safety data both by treatment group and overall.

Clinical Laboratory Values

All laboratory test results will be summarized by period together with the change from baseline. The frequency distribution for low/normal/high or normal/abnormal will be summarized as well. The denominators for calculating the percentages will be based on the number of subjects with non-missing values in the Safety Population.

Vital Signs

Vital sign results will be summarized by period, together with the change from baseline.

Physical Examination

Summaries of physical examinations will present frequency distribution of abnormal findings by body system and period. The denominators for calculating the percentages will be based on the number of subjects evaluated for a particular body system of each dose level in the Safety Population.

Electrocardiogram (EKG)

EKG findings will be classified as normal vs abnormal. The number and percentage of each category will be summarized using frequency table for each period. The denominators for calculating the percentages will be based on the number of subjects with non-missing values in each period.

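### Section 11.3 summarises EKG as an unpaired normal/abnormal percentage per period, so new abnormalities can be offset by resolved ones in that table

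*Combined protocol and SAP*

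**What the plan says.** Section 2.1 lists EKG among the safety assessments: "Safety endpoints will include adverse events as evaluated with subject self-reporting, vital signs, clinical chemistry and hematology blood analyses, urinalysis, and electrocardiogram (EKG"). Appendix 2 schedules an EKG at all five visits. Under Section 6, subjects who stop early complete the Visit 4 assessments, which include a 12-lead EKG.

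The EKG analysis in Section 11.3 is three sentences long:

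- The first sets the variable: "EKG findings will be classified as normal vs abnormal".
- The second sets the display: how many subjects, and what share of them, fall into either class, shown period by period.
- The third sets the base for those shares: "The denominators for calculating the percentages will be based on the number of subjects with non-missing values in each period".

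The same section treats the other measured safety data differently. For laboratory values, "All laboratory test results will be summarized by period together with the change from baseline". For vital signs, "Vital sign results will be summarized by period, together with the change from baseline". It names no change from baseline, shift table or new-onset count for EKG.

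The general rule for categorical variables in Section 11.2 is also counts and percentages only. That section leaves further detail to a separate SAP, which is not in the file.

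**The concern.** A percentage abnormal in each period is a marginal quantity. Its change over time equals new abnormalities minus resolved ones, so a flat percentage fits both no change in anyone and a real number of new abnormalities offset by resolutions. A safety reader wants the first of those two components, not the difference.

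This matters more here than in a controlled trial, where an unpaired table at least allows a comparison between arms. Here there is one open-label arm, and the only in-study reference for an EKG is the same subject's pre-treatment tracing. The paired readings will exist, but the stated summary does not pair them.

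The unit of analysis is also open. The Fixed Dose Period contains the EKGs at Visits 2, 3 and 4, and the plan does not say whether a subject's category for that period is the worst, the last or each reading. The pre-dose Visit 1 EKG sits in the Dose Escalation column of Appendix 2.

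**Working it through.** **Plan's own figure.** The plan states no figure for EKG. Its only safety calculation (Section 11.7) is the chance of seeing at least one case of a 5% event in 50 subjects: 1 − 0.95^50 = 0.923, which reproduces the stated 92%. It says nothing about how an EKG change would be displayed.

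**Inputs**

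- N = 50 subjects (Section 4).
- A = number abnormal at baseline. The documents give none. *Assumption:* 30% (A = 15), with a range of 10% to 50%.
- n = number newly abnormal and r = number resolved. *Illustration:* 5 each.
- No dropout, to isolate the netting.

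**Formulas**

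- Percentage abnormal before: A / N
- Percentage abnormal after: (A − r + n) / N
- Change the planned table shows: (n − r) / N
- New-abnormality rate: n / (N − A)

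**At the 30% assumption**

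- Before: 15/50 = 30%
- After: (15 − 5 + 5)/50 = 15/50 = 30%
- Change shown: (5 − 5)/50 = 0
- New-abnormality rate: 5/(50 − 15) = 5/35 = 14.3% (exact 95% CI 4.8% to 30.3%)

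The same display, 15/50 both times, also fits no change in anyone: 0/35 = 0% (exact 95% CI 0% to 10.0%). The planned table cannot tell these two cases apart; a table of baseline by later category can.

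**Across the assumed range, still with 5 new and 5 resolved**

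| Abnormal at baseline | A | N − A | Later percentage shown | New-abnormality rate |
|---|---|---|---|---|
| 10% | 5 | 45 | 10% | 5/45 = 11.1% |
| 20% | 10 | 40 | 20% | 5/40 = 12.5% |
| 30% | 15 | 35 | 30% | 5/35 = 14.3% |
| 40% | 20 | 30 | 40% | 5/30 = 16.7% |
| 50% | 25 | 25 | 50% | 5/25 = 20.0% |

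At 10% the example needs every baseline-abnormal subject to resolve, so that row is an extreme. Exact equality of n and r is not essential. With 5 new and 3 resolved at the 30% assumption, the table moves from 15/50 = 30% to 17/50 = 34%, a rise of 4 points, while the new-abnormality rate is still 14.3%.

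**The case against.** The best defence is that this table is not the only route by which an EKG change can surface.

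- **Listings.** Section 11.3 also promises individual listings of safety data. That stands, although a reader would have to rebuild the pairing by hand from up to 50 × 5 = 250 scheduled EKGs.
- **Adverse events.** Section 10.6 counts an event as treatment-emergent if it is new or worse than before treatment, which is a within-subject rule that does not net. Section 10.9 lets an unfavourable sign be recorded as an adverse event. Section 2.1 can itself be read as naming EKG as a means of detecting adverse events. This also stands, but the route depends on investigator judgment. Section 10.7 requires clinically significant laboratory values to be entered as adverse laboratory events; no matching rule for EKG appears.
- **Separate SAP.** It could add a shift table. But Section 11.3 does not defer the EKG method; it states one, and the general rule in Section 11.2 would give the same table.

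Three stronger readings are tempting, and the documents do not support them.

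- **EKG changes would be invisible in this trial.** They could be hidden in the summary table only, for the reasons above.
- **Dropout adds materially to the masking.** Early leavers are due an EKG, and the denominator is per period, so a subject who leaves after Visit 2 can still contribute a fixed-dose reading. Dropout that is proportional to baseline status hides nothing unless some abnormalities also resolve. Hiding 5 new cases through dropout alone would need, for example, 8 of 10 leavers to come from the 15 abnormal subjects. If leaving is unrelated to EKG status, the chance of 8 or more is 4,007,003/10,272,278,170, about 0.04%.
- **The laboratory category tables share the fault.** They are an addition ("The frequency distribution for low/normal/high or normal/abnormal will be summarized as well"). Laboratory results already have a change from baseline and the reporting rule in Section 10.7.

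**Conclusion.** The point holds for the EKG summary table. As written, it reports a net movement and cannot show how many subjects became abnormal on treatment. With 5 new and 5 resolved among 50, it shows no change while 14% of baseline-normal subjects became abnormal at an assumed 30% baseline rate, and 11% to 20% over assumed rates of 10% to 50%.

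These figures show what the table can conceal; they do not predict what will happen. They rest on the assumed baseline rate, on some abnormalities resolving, and on the separate SAP following the protocol text. The safety analysis as a whole is not blind to EKG changes, because listings and adverse event tables remain. The change is still worth making: the stated method is weaker than one that uses the same EKGs.

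**What to change.** Add the following to the EKG summary, in the SAP and preferably in Section 11.3:

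1. **Define baseline.** Use the Visit 1 EKG. Section 3.1 lets subjects who roll over within 14 days of ENT-01-030 Visit 6 skip procedures common to both studies; where the Visit 1 EKG is not repeated for that reason, use the Visit 6 EKG.
2. **Tabulate shifts.** Give a within-subject table of baseline category by category at each later visit, and by the worst on-treatment EKG. Include early-termination EKGs. This also settles which reading represents the Fixed Dose Period.
3. **Headline new abnormalities.** Report the number and percentage newly abnormal among subjects normal at baseline, with an exact confidence interval.

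The per-period percentages can stay alongside. A two-category shift table will not show deterioration in a subject already abnormal at baseline. The protocol does not describe collecting a comparative reading for that, so it stays with the listings and adverse event reporting.

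The cost is SAP wording and table shells. All the EKGs needed are already scheduled; subjects without a repeated Visit 1 EKG also need their Visit 6 result carried over from ENT-01-030.
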